#### 9.1.5.3 *Insecticide resistance monitoring*

1. Insecticide resistance monitoring will be examined at the end of years one and two and will include testing dinotefuran, permethrin, and either deltamethrin or alphacypermethrin.
2. *An. gambiae s.l.* mosquitoes will be collected as larvae while *An. funestus* will be collected as adults from inside houses. Fed/gravid *An. funestus* will be allowed to lay eggs. Immature mosquitoes collected as larvae or from adult *An. funestus* will be reared to the adult stage in the insectary at the KEMRI CGHR in Kisian.
3. Adults that are 2-5 days old will be exposed to the insecticides using standard WHO tube tests to permethrin, deltamethrin and alphacypermethrin [21].
4. Twenty to twenty-five mosquitoes per tube (or bottle) will be run, and enough tubes/bottles will be run to have a minimum of 100 mosquitoes exposed (the total number of mosquitoes will be dependent on the amount able to be collected).
5. WHO test papers for dinotefuran are not available. Resistance testing for this insecticide will be done using a topical application of a diagnostic concentration to the thorax of adult mosquitoes, and mortality will be recorded after 24 hours.

#### 9.1.5.4 Bait station durability

1. To examine the durability of the bait stations during the first 6-month deployment, a selection of ATSBs will be randomly sampled from households within ATSB study clusters. Stations collected from households will be immediately replaced with new stations.
2. The bait station will be placed in a 30cm x 30cm x 30cm cage and 100 female *An. gambiae* or *An. arabiensis* (collected as larvae and reared in the lab) will be introduced into the cages after an appropriate period of starvation.
3. Mortality will be recorded at 24 hours.
4. The number of dead and live mosquitoes will be recorded at 48 hours.

#### 9.1.5.5 Entomological laboratory procedures

1. Specimens will be processed to estimate species composition, density, age structure, sporozoite rate, and EIR estimation.
2. Mosquitoes will initially be identified morphologically using standard dichotomous keys
3. All female anopheline mosquitoes will be tested for the presence of *Plasmodium spp.* sporozoites using ELISA
4. Mosquitoes identified as *An. gambiae* s.l. will be identified to species using standard PCR. A subset of *An. funestus* will be identified to species by standard PCR methods.
5. A subset of live female mosquitoes collected by UVLT or HLC will be dissected and examined for dilatations in the ovarian duct as a proxy for age (each dilatation represents an egg batch laid).

[figure not shown]
#### 9.1.6 ATSB Intervention monitoring

1. ATSB monitoring assistants will be trained on proper installation, adjustment, and removal and transport of ATSBs on structure walls, administering an ATSB questionnaire, and responding to questions or concerns raised by household members.
2. After administering informed consent and ATSB installation community-based, ATSB monitors will visit households in intervention clusters on a monthly basis
3. ATSB monitors will complete a questionnaire programmed onto a tablet or electronic data capture form to assess the presence of each ATSB and/or whether it has incurred any damage
4. If an ATSB has been damaged, the monitor may photograph the damaged ATSB
5. Damaged or missing ATSBs will be replaced by ATSB monitors at each visit
6. ATSB monitors will instruct the head of the household to contact the study team if an ATSB is damaged or is missing between each visit so that the ATSB monitor can return to replace it to ensure high ATSB coverage rates
7. ATSB monitors will additionally respond to any questions or concerns that household members have about the ATSB or the trial. They will refer questions they are unable to answer to the field supervisor for further consideration and response.

#### 9.1.7 Rapid ethnographic methods

The qualitative component of this study is designed to understand potential factors that influence coverage, including 1) ASB and ATSB coverage, defined as the continuous and correct installation of the ATSBs, and 2) LLIN coverage, defined as routine use by household members each night (see Figure 6: Conceptual framework for the qualitative study, below).

Figure 6: Conceptual framework for the qualitative study

A series of three qualitative evaluations will be conducted as part of this trial: 1) after an entomological validation trial with ASBs, but before the main trial, 2) during the first year of the ATSB main trial, and 3) during the second year of the main ATSB trial. For the evaluation occurring during the main trial, these will be conducted at least 1-month after the introduction of the ATSBs. Focus group discussions (FGD) and in-depth interviews (IDI) will be conducted in intervention clusters (for the first evaluation, these will occur in areas where ASBs had been implemented for entomological validation trials) with the aim of understanding the potential factors influencing coverage. These qualitative methods will be applied as rapid ethnographic methods with a focus on rapidly available and actionable information to inform programmatic decisions. This includes guiding community engagement prior to the first ATSB deployment and informing strategies to ensure high community engagement and coverage levels throughout the trial. The FGDs will engage a set of community members as key informants in a discussion regarding community experiences with the ASBs and ATSBs. Separate FGDs will also be conducted with ASB and ATSB monitoring assistants serving as key informants on community experiences. The IDIs will be conducted with residents in intervention areas and will be used to explore in detail the experience of individual households with the ASBs and ATSBs. Additional messages will be created from these ethnographic methods to provide similar messages across arms to ensure LLIN usage and strengthen education and care-seeking behaviour for malaria.

#### 9.1.7.1 Procedures for focus group discussions

1. Field workers will receive training in the study design, research tools, and study procedures for the FGDs and IDIs.
2. FGDs will be performed in each of the entomological validation clusters at baseline
3. ATSB monitoring data will be used during the main trial to classify clusters as having a relatively high or low incidence of ATSB damage, removal or replacement.
  - a. Three clusters classified as high incidence and three clusters classified as low incidence will be randomly selected
  - b. A single village within each of these six clusters will be randomly selected

4. Within each of the clusters/villages selected for FGDs, two groups of six to eight community members will be purposively selected by community-based field monitoring assistants based on their activity within the community and exposure to views and experiences of community members (i.e. school teachers, religious leaders, village elders)
5. Additionally, at each round, two sets of FGDs will be conducted with six to eight community-based ATSB monitoring assistants selected by the research team as key informants with monitoring ATSBs and deploying them
6. FGDs will be segregated by sex, and an equal number of FGDs with women and men will be conducted
7. Participants selected for FGD will be brought together in a central but private location and provided with an overview of the study and an informed consent form. Those that provide informed consent will continue to participate in the discussion.
8. The FGD will be closed to outside observers, limited only to consenting participants and the fieldworkers conducting the session.
9. Two field workers will conduct the FGD. One fieldworker will lead the discussion, and the other will take notes. The discussion will be recorded for transcription.
10. A semi-structured discussion guide will be used to guide the discussion (See separate file, ATSB Focus Group Discussion Guide (Community Members) and (Monitoring Assistants)).
11. The discussion will last approximately 60 minutes.
12. The recording of the discussion will be used to create a discussion transcript for data analysis.

#### 9.1.7.2 *Procedures for in-depth-Interviews*

1. The first round of IDIs will be conducted among four key informants per each of the entomological validation and field trial study clusters. The four participants will be purposively selected using community-based field workers that assisted with the monitoring and implementation of the validation study. The field workers will be asked to select two households that experienced issues with the ASB, including damage, removal, or replacement, and two households that did not experience such issues.
2. One fieldworker will visit each selected potential IDI participant and will provide information about the study. The participant will be asked to provide informed consent. The interview will be conducted with people who provide informed consent.
3. The interviewer will use a semi-structured interview guide to guide a discussion that will last approximately 60 minutes.
4. The interview will be recorded for transcription.
5. The recording of the interview will be used to create a discussion transcript for data analysis.
6. Subsequent rounds of IDIs will be conducted during the trial. Twelve IDIs will be conducted within the 6 study clusters identified for FGDs as described above. Informants will be identified according to the procedures noted above. Within each cluster, the study team will seek one informant from a household that experienced ATSB issues and one informant from a household that did not experience these issues. The interviews will be conducted according to the procedures outlined above.

Data for FGDs and IDIs will be analysed thematically and may use software including Atlas.ti and NVivo for data organization and analysis.

### **9.1.8 Economic evaluation**

ATSB product and delivery cost data will be collected and combined with efficacy measures of clinical malaria incidence to produce incremental cost-effectiveness ratios (ICER). The ICER will

represent the incremental cost-effectiveness of the use of ATSB in addition to standard of care malaria vector control (high/universal LLIN coverage) to estimate the financial and economic costs of the intervention. Cost data will be combined with efficacy estimates to produce cost-effectiveness estimates of this strategy from a provider perspective.

#### 9.1.8.1 *Procedures*

Cost data collection will include a review of program records and reports, invoices, budgets, expenditure reports, as well as through interviews with intervention implementers to acquire information not recorded in existing program data. No interaction with study participants is required for provider perspective cost analysis. Interviews only with trial staff will be focused on resource use during the implementation of the study interventions. Where direct estimates of unit costs for inputs are not available through the above methods, data on costs will be supplemented with secondary source data such as is available from the WHO-CHOICE database, the World Bank, the International Monetary fund or other published literature. Economic costs will be estimated, meaning that costs from donated inputs will also be valued.

#### 9.1.8.2 *Timeframe*

The collection of cost data will be conducted throughout the study period, with a review of cost data occurring quarterly throughout the scale-up and roll-out of the intervention and study. Final cost estimates and cost-effectiveness calculations will be done at the conclusion of the study.

## 9.2 DATA MANAGEMENT

The sections below provide details of data management for individual study components. All data will be stored on a secure, shared drive managed by KEMRI and backed up on a secure server at LSTM, Liverpool, UK. All investigators and the sponsor, IVCC, will have access to the data.

### 9.2.1 ATSB monitoring, cohort and cMIS case report forms

The questionnaire will be administered using electronic data capture forms on mobile phones or tablets. The data will be sent to a cloud-based secure server on a daily basis. Data will be extracted from the server after each round of ATSB monitoring is completed. The extraction will be completed using Alteryx, Microsoft Excel, or Microsoft Access, and data will be loaded into a package for statistical analysis such as Stata and/or SAS and/or R.

### 9.2.2 Passive case detection

Data entered into routine outpatient, ANC, and CHV MoH Registers will be extracted using ScanForm software and stored on a secure cloud-based server (under separate protocol).

### 9.2.3 Rapid ethnographic methods: FGD and IDI data

Transcripts of all discussions and interviews will be created in Microsoft Word. Interviews will be translated into English during the process of transcription. Data coding and analysis will be completed using Microsoft Excel.

### 9.2.4 Entomological monitoring

Field data will be recorded using electronic data capture forms on mobile phones or tablets. This will include details on the house structure (e.g., roof type, wall type, open or closed eaves), presence and use of LLINs, the timing of any IRS application within the last 12 months, and other factors that may affect mosquito density (e.g., cooking in the house, use of mosquito coils, presence of animals). Laboratory data will be entered using a standardized data entry form either directly on a PC or a

tablet. Data will be imported into Microsoft Access, and data merging, cleaning, and analysis will be done using a standard statistical software package such as SAS, Stata or R.

### 9.2.5 Economic evaluation

Data will be stored in the manner collected and collated into Microsoft Excel then transferred to R software for analysis. Transcripts of interviews with program staff will be created in Microsoft Word. All data will be backed up in a password-protected secure cloud storage setting to prevent data loss.

## 9.3 BIOLOGICAL SAMPLES

### 9.3.1 Blood samples

During cohort and cMIS household visits, a finger- or heel-prick blood sample (approximately 500 µL) will be taken to prepare dried blood spots (DBS) on filter paper. DBS will be used to evaluate malaria positivity or exposure through molecular and serological methods as well as exposure to mosquito biting at a later date and will not be used for clinical care. Should the participant be febrile at the time of the visit (axillary temperature  $\geq 37.5^{\circ}\text{C}$ ) or report a fever in the previous 48 hours, a malaria RDT will also be performed. RDT results will be used for treatment decisions based on the Kenya Ministry of Health guidelines. In certain cases, to confirm parasite clearance, a blood smear may be prepared to perform light microscopy.

Real-time quantitative PCR will be performed on cohort samples to evaluate the time to first infection and may be performed on a sub-sample of cMIS samples to evaluate malaria prevalence. Should funds be available, PCR may also be performed to assess parasite genetics, including complexity of infection analyses to evaluate the impact of ATSB on circulating parasite strains.

Serological studies may be performed on cohort and cMIS samples to evaluate changes in exposure to malaria-associated with ATSB implementation as evaluated through antibody profiles of the participants. These may include IgG antibodies to antigens such as merozoite surface protein (MSP-1), apical membrane antigen (AMA-1), circumsporozoite antigen (CSP), and other antigens. Additionally, exposure to vector biting may be assessed by measuring antibodies to mosquito saliva antigens, including Sg6 in the blood.

In other geographic areas such as Eritrea, HRP2 deletions have been identified. As the RDTs that are used in Kenya are based on HRP2 detection, the main trial outcomes rely on the detection of HRP2 antigens. Preliminary data from the study site (unpublished data 2018) have not identified evidence of HRP2 deletions. We may assess HRP2 concentration levels and PfHRP2/3 deletions from both cohort and cMIS samples.

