## 5 OBJECTIVES AND OUTCOMES

Table 1: Objectives and outcomes

5.1 PRIMARY OBJECTIVE AND OUTCOME	
Primary objective	Primary endpoint
To determine if ATSB deployment plus universal LLIN coverage is superior to universal LLIN coverage alone in reducing the case burden of clinical malaria in western Kenya	
 
The incidence rate of clinical malaria by the end of year-2, defined as current fever (axillary temperature of <math>\geq 37.5^{\circ}\text{C}</math>) or history of fever in last 48 hours and a positive rapid diagnostic test (RDT, pLDH or HRP2), in children aged 1-<15 years enrolled in the cohort study
 

5.2 SECONDARY OBJECTIVES AND OUTCOMES	
5.2.1 Efficacy	
Secondary objectives	Secondary endpoints
To determine if ATSB deployment plus universal LLIN coverage compared to universal LLIN coverage alone is superior in reducing malaria infection	
 
The time to first malaria infection assessed by PCR by the end of year-2, in children aged 1-<15 years enrolled in a cohort study
 
The incidence rate of malaria infection detected by RDT (pLDH) by the end of year-2, in children aged 1-<15 years enrolled in a cohort study
 
The prevalence of malaria infection diagnosed by RDT in continuous household surveys in participants aged <math>\geq 1</math> month.
 

To determine in ATSB deployment plus universal LLIN coverage compared to universal LLIN coverage alone reduces the clinical case burden in health facilities and communities	
 
The incidence rate of RDT or microscopy confirmed clinical malaria assessed through passive surveillance at health facilities and community-based surveillance by Community Health Volunteers serving the village-clusters
 

To determine if the rate of overall illness events differs in the ATSB deployment plus universal LLIN coverage arm when compared to the control arm	
 
The incidence rate of non-malaria illness in the cohort study
 
The incidence rate of all-cause sick visits assessed through passive surveillance at health facilities and community-based surveillance by community health volunteers
 

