#### 6.3.3.3 *Continuous malaria indicator household surveys (cMIS)*

Malaria prevalence data will be obtained from ongoing continuous (year-round) malaria indicator surveys (cMIS) under an existing protocol (SSC 2773; LSTM Protocol 14.009; CDC Protocol 6733). As part of these surveys, fingerprick blood samples are collected for malaria RDTs and dried blood spots for later molecular and serological testing. Participants testing RDT positive are treated according to the Kenya Ministry of Health guidelines. A questionnaire is administered to the selected individual or their caretaker to evaluate key contextual variables, including human behavioural factors, demographic characteristics, and travel patterns. Please see Section 9.1.3, Continuous household survey, page 36 for more details.

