### 7.8.2 Continuous malaria indicator survey to assess malaria parasite prevalence

#### 7.8.2.1.1 *Main trial*

The continuous malaria indicator survey (cMIS), conducted under a separate protocol, provides adequate power to detect a 30% reduction in the all-age malaria prevalence detected by RDTs per year from 29.0% to 20.3%. The 29% prevalence is based on the observed all-age prevalence in Rarieda sub-county (29%) (representing two-thirds of the study area) and in Alego-Usonga (47.3%), representing one-third of the study area. The 47.3% in Alego-Usonga is based on cMIS data in neighbouring Karemo. The prevalence estimate in Rarieda is reduced from 29% to 27.7% to account for a 50% drop in malaria prevalence in children < 5 years of age who will receive the RTS,S vaccine. Because this age group only represents 13.9% of the population, the anticipated impact of RTS,S on the all-age prevalence in Rarieda is modest. The pooled estimate of the RTS,S adjusted all-age prevalence of 27.7% in Rarieda and 47.3% in Aleg-Usonga is 34.1%. We propose to use a more conservative prevalence of 29% to allow a 15% reduction in malaria prevalence due to annual variations in environmental conditions (e.g. rainfall, temperature) ( $0.85 \times 34.1\% = 29\%$ ). This requires 3,520 participants per year (44 per cluster, including 9 non-responders and 35 responders) (ICC=0.05, power=90%, two-sided alpha=0.05, and assuming 20% non-responders, e.g. refusals, not at home, etc.). The values for the intra-cluster correlation (ICC), parasite prevalence, and non-response rates were estimated from the ongoing cMIS study. Where possible, households that are included in the first year will be excluded in the second year. Over 2-years, and assuming no overlap in participants between the first and second year, a sample size of 88 per clusters (including 18 non-responders and 70 responders) would provide 80% power to detect a 23.7% reduction or 90% to detect a 27.3% reduction (ICC=0.05, alpha=0.05). Similarly, 70 responders per cluster after two years would provide 80% power to detect a 30% reduction if the ICC is 0.091 instead of 0.05, or 90% power if the ICC is 0.064.

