### 9.1.3 Continuous household survey

#### 9.1.3.1 Continuous malaria indicator survey (cMIS)

Community malaria infection prevalence will be evaluated through an ongoing protocol involving participants of all ages, “Malaria Indicator Household Surveys to evaluate the impact of malaria transmission reduction activities in Siaya County, western Kenya: a continuous rotating panel survey”; short title, “Continuous Malaria Indicator Survey (cMIS)” [KEMRI SERU Protocol# 2773; CDC IRB# 6733; LSTM REC# 14.009; PATH RDC# 0777]. The survey will include malaria blood testing by RDT and PCR. The RDT result will dictate malaria treatment in the field, and PCR results will be processed at a later date to estimate the secondary outcome of infection prevalence by PCR. The individual and household questionnaires will capture information about malaria intervention coverage (e.g. LLIN ownership and use), housing characteristics, and household demographic information. The surveys will also measure a set of indicators regarding ATSB knowledge and perceptions.

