#### 9.1.3.2 Brief description of cMIS procedures

- Households are randomly selected for household visits

- Staff members administer informed consent
- Staff members administer the cMIS questionnaire on a password protected study tablet, which includes questions about the history of illness, care-seeking, malaria prevention methods and coverage
- Study staff collect blood (250 µL to 1 mL) from a finger- or heel-prick to prepare approximately five blood spots on filter paper and to perform a rapid diagnostic test. If the RDT is positive, the study staff member treats the participant per Kenya Ministry of Health guidelines

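### Section 9.3.1 makes the RDT at survey visits conditional on fever, which conflicts with the survey procedures and with the RDT prevalence endpoint; PCR prevalence is also called a secondary outcome without being listed as one

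*Protocol*

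**What the plan says.** **Endpoint and power.** Table 1 (Section 5) lists as a secondary endpoint "The prevalence of malaria infection diagnosed by RDT in continuous household surveys in participants aged" one month or more. Section 6.1 says the prevalence surveys are powered on RDT prevalence each year. Section 7.8.2.1.1 says the survey "provides adequate power to detect a 30% reduction in the all-age malaria prevalence detected by RDTs per year from 29.0% to 20.3" per cent, and adds: "This requires 3,520 participants per year (44 per cluster, including 9 non-responders and 35 responders"). The inputs given are ICC 0.05, 90% power, two-sided alpha 0.05 and 20% non-response.

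**Who is tested by RDT.** Section 6.3.3.3 says that in the surveys "fingerprick blood samples are collected for malaria RDTs and dried blood spots for later molecular and serological testing". Section 9.1.3.2 has staff take blood "to prepare approximately five blood spots on filter paper and to perform a rapid diagnostic test". Neither sets a fever condition, and nor does the household-survey row of Table 7. Section 9.1.2.1 requires an RDT for every child at cohort enrolment. Section 9.3.1 begins "During cohort and cMIS household visits, a finger- or heel-prick blood sample" and describes dried blood spots without any condition. It then says that if the participant has a raised temperature "or report a fever in the previous 48 hours, a malaria RDT will also be performed".

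**PCR.** Section 9.1.3.1 says the survey tests by RDT and PCR, and that "PCR results will be processed at a later date to estimate the secondary outcome of infection prevalence by PCR". Table 1 has no PCR prevalence outcome. Section 9.3.1 describes PCR on survey samples only as a possibility, and then on a sub-sample.

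**The concern.** The only place that states a specimen rule jointly for cohort and survey visits ties the RDT to current or recent fever. Read as it stands, an afebrile survey participant gives dried blood spots but has no RDT. The survey would then estimate RDT positivity among febrile people. That is a different quantity from infection prevalence, because infections without fever drop out of both numerator and denominator. The missing RDT results could not be recovered later.

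The effect would reach beyond one secondary endpoint. Survey prevalence is a baseline summary measure (Table 2), is among the baseline data meant to inform restricted randomisation (6.3.2), and is a listed covariate for the adjusted analysis of clinical incidence (9.4.3.3). The same sentence also clashes with the enrolment RDT in 9.1.2.1, on whose result the two-week visit in 9.1.2.2 relies when a child is febrile.

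The PCR wording is a separate and smaller matter. The protocol disagrees with itself on whether PCR prevalence is a secondary outcome, and on whether the survey samples will be tested for it.

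**Working it through.** **Inputs.** From 7.8.2.1.1: prevalence 29.0% against 20.3%, ICC 0.05, two-sided alpha 0.05, m = 35 responders per cluster, 20% non-response. From 7.8.1.1: 40 clusters per arm.

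**Step 1: the plan's own figure.**
- Design effect = 1 + (m − 1) × ICC = 1 + 34 × 0.05 = 2.70.
- Effective n per arm = 40 × 35 / 2.70 = 518.5.
- SE of the difference = √[(0.29 × 0.71 + 0.203 × 0.797) / 518.5] = √(0.3677 / 518.5) = 0.0266.
- Unpooled: 0.087 / 0.0266 − 1.96 = 1.31, power 90.4%. With pooled variance under the null, power is 90.3%.
- With non-response: 35 / 0.8 = 43.75, so 44 per cluster and 44 × 80 = 3,520.

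The stated sample size and power reproduce. The two-year figures do as well (pooled): 79.9% for a 23.7% reduction, 90.1% for 27.3%, 80.1% at ICC 0.091 and 90.2% at ICC 0.064.

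**Step 2: the procedures side by side.**

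| Section | Setting | RDT rule |
|---|---|---|
| 6.3.3.3 | survey | no fever condition |
| 9.1.3.2 | survey | no fever condition |
| 9.1.2.1 | cohort enrolment | every child |
| 9.1.2.3 | monthly cohort visit | only with current or recent fever, stated explicitly |
| 9.3.1 | cohort and survey visits | stated only for current or recent fever |

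The fever condition in 9.3.1 is the rule of 9.1.2.3. It fits the monthly cohort visit and neither survey visits nor enrolment.

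**Step 3: what fever-only testing would do to the survey.** The protocol gives neither the febrile share f nor the positivity among febrile people, so both are assumptions. The number tested per cluster is 35f, the design effect is 1 + (35f − 1) × 0.05, and the relative reduction stays at 30% (pooled variance).

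| Febrile share (assumed) | Tested per cluster | Design effect | Effective n per arm | Power, 29% positivity | Power, 45% positivity (assumed) |
|---|---|---|---|---|---|
| 10% | 3.5 | 1.125 | 124.4 | 36% | 59% |
| 20% | 7 | 1.30 | 215.4 | 55% | 82% |
| 30% | 10.5 | 1.475 | 284.7 | 67% | 91% |
| 50% | 17.5 | 1.825 | 383.6 | 80% | 97% |

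If untested people were instead counted as negative, control prevalence at 29% positivity would be f × 29%, that is 2.9% to 14.5% over the same shares, and power would be 15% to 57%. In every row the quantity estimated has changed, whatever the power.

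**Step 4: PCR.** With the same ICC and a 30% relative reduction, PCR in all 35 responders gives 90.3% power if PCR prevalence is 29%, 96.0% at 35% and 98.4% at 40% (assumed prevalences). On a sub-sample at 29%, power is 86.9% with three quarters tested, 80.0% with half and 62.1% with a quarter.

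**The case against.** The strongest reply is that the sections written for the survey already settle the matter. Sections 6.3.3.3, 9.1.3.1 and 9.1.3.2 describe an RDT without a fever condition, Table 7 agrees, and the survey runs under a separately approved protocol. Section 9.3.1 is a specimen summary. It says an RDT is also done in febrile participants, and does not say that others go untested; where the protocol means that, in 9.1.2.3, it says so for cohort members. The sentence about smears that closes the same paragraph concerns parasite clearance, a cohort procedure. A cohort rule carried into a paragraph covering both components is the likeliest explanation.

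Most of this stands. It makes a slip of wording far more likely than an intended change, and nothing shows that field staff would skip RDTs in afebrile survey participants. It does not remove the conflict. This protocol adopts survey RDT prevalence as its own endpoint and writes its own specimen rule for survey visits, and that rule makes no provision for an RDT in the afebrile.

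A reader might infer three stronger claims that the documents do not support:
- *That the endpoint has three rival definitions.* The registration table, Table 1, 6.1 and 7.8.2 all name RDT prevalence. Section 9.1.3.1 adds PCR to RDT testing and does not replace it.
- *That 90% power holds under one reading only.* PCR in all responders would also reach 90% at a PCR prevalence of 29% or more, given the same ICC and relative effect, and fever-only testing reaches 91% at 30% febrile and 45% positivity.
- *That this is the only secondary endpoint with a power statement.* Mosquito density has one in 7.8.3.

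**Conclusion.** The protocol is wrong as written in its testing procedures, not in its endpoint definition. If 9.3.1 were applied at survey visits, it would replace infection prevalence with positivity among febrile people. The sample-size calculation is sound and is shown for RDT in all 35 responders per cluster; no power has been shown for fever-only RDT or for PCR. The reduced-power figures illustrate the possible scale and rest on febrile shares and positivity that the documents do not give, so they are not estimates of what the trial would see.

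The status of PCR prevalence is inconsistent across 9.1.3.1, Table 1 and 9.3.1. It might be inferred that a PCR result could silently take the place of the RDT result. That goes too far, because RDT prevalence is prespecified in both endpoint tables.

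The correction is worth making because a stated rule, if followed, would defeat a powered secondary endpoint.

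**What to change.** 1. In 9.3.1, limit the fever-conditional RDT sentence to scheduled cohort follow-up visits, and refer to 6.3.3.3 and 9.1.3.2 for the survey and 9.1.2.1 for cohort enrolment. Outcome ascertainment in the survey then matches the RDT prevalence endpoint.
2. Reconcile 9.1.3.1, Table 1 and 9.3.1 on PCR prevalence. Either list it in Table 1 as an additional secondary outcome and state which survey samples are tested, or label it exploratory in 9.1.3.1. Both are acceptable; in either case keep RDT prevalence as the powered survey endpoint.

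The cost is a few sentences of protocol wording, submitted as an amendment under 11.2.2. The RDT change adds no tests beyond those already planned in 9.1.3.2 and 9.1.2.1. The sample size does not change. Listing PCR as a secondary outcome would commit the trial to PCR testing that is now optional; labelling it exploratory would not.
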